#### **5.4 Blood draws**

During the screening visit, all participants will have a blood draw to test for CRP levels to stratify the participants accordingly in High CRP and Low CRP groups. Participants will also have a blood sample drawn at the end of the screening visit to test immediately for Hepatitis B and C, HIV, autoimmune diseases (double-stranded DNA test), and rheumatoid factor; as well as to use in later analyses of inflammatory markers. Participants will have a blood sample drawn (approximately 16.5mL) at the screening visit, approximately 40 mL at the baseline visit, approximately 40 mL at the end of the study, 40 mL at the end of the open label phase. Blood samples will be used for doing tests for inflammatory markers and for measuring levels of Interleukin-6, Interleukin-10, TNF-alpha, and C-reactive protein. We will look at immunological markers by two methods; luminex and flow cytometry. The Luminex assay measures soluble proteins in the sera. Molecules such as IL-6 and TNF-alpha, MIP1-alpha, IFN-alpha, CRP will be assessed. We will include or alter molecules in the luminex assay based on the most recent literature as we near the end of sample collection. Flow cytometry will also be utilized. Flow cytometry will be used to measure the status of T cells which are important in suppressing such conditions as infectious disease and cancer. We will develop a series of markers that define the memory and naive phenotype of T cells along with their activation status and functionality. We will also assess additional cell subsets such as NK and macrophages. Molecules that will be assessed include but are not limited to; CD3, CD4, CD8, CD45RO, CD27, CCR7, CD69, CD33, CD68, CD56, CD16, CD38 and HLADR and CD11c -monocytes. Some blood will be retained and banked for future research. Additional blood is being collected for ex vivo isolation of human peripheral blood mononuclear cells (PMBC), which is another assessment of inflammation levels. This additional blood draw will be optional and offered to all depressed participants.

Participants will give blood for a liver-function test and for hematocrit levels to test for GI bleeding. Participants may also have 24-hour ambulatory blood-pressure monitoring. Participants may wear a cuff for 24 hours that is set to automatically take blood pressure every 15 minutes during the day and every 30 minutes during the night.

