hypertensive responses to COX-2 selective inhibitors were reported to be more likely in patients with elevated blood pressure as a pre-existing condition (23).

A number of retrospective studies, RCTs, and database studies, as recently reviewed (24), suggest that SSRIs including escitalopram have an overall neutral impact on the cardiovascular system including blood pressure. In a randomized clinical trial using fixed-dose escitalopram, 10 mg/d, over a period of 8 months, hypertension was the reason for discontinuation in only n=2 out of n=274 (0.7%) escitalopram-treated patient (25).

Age has an physiological effect on the glomerular filtration rate (GFR), quantified as a decline in GFR by 0.4 ml/min/year (26). COX-2 inhibitors' renal effects are a decline in the GFR (27) and an alteration of the feedback mechanism which controls renin release (28). Thus, the noted increase in aldosterone concentrations after escitalopram administration - 261±36 pmol/liter at baseline, 269±38 pmol/liter at 2 weeks, and 282±40 pmol/liter at 6 weeks (p=0.04) (29), by itself functionally not associated with changes in blood pressure in this study of normotensive males with depression (29) - might sensitize the reno-vascular system for hypertensive responses under conditions of celecoxib co-administration.

Taking the consideration outlined above into account, **our initial strategy to mitigate this risk was to identify the patients responding to celecoxib administration with an above average increase in blood pressure. The paradigm to detect such an above average signal was the use of continuous 24-hour ambulatory blood pressure monitoring (ABPM) before the start of their enrollment to establish a baseline, and under steady state conditions of celecoxib plasma drug concentrations, i.e. one to two weeks after start of the study; ABPM at the end of the study was planned to collect further safety and interventional data. Patients demonstrating an elevation of 10 mmHg in mean daytime and nighttime systolic blood pressure at 1-2 weeks after the start of the study compared to the mean daytime and nighttime systolic blood pressure at baseline and the mean daytime (that is out of bed times) systolic blood pressure is  $\geq 150$  mmHg were instructed to discontinue trial medication and excluded from the study and instructed to see their primary care physician for further evaluation and follow up.**

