**However, using this initial strategy we were only able to enroll n=2 patients during the past 2 years, concluding that the in-/exclusion criteria and protocol procedures, in particular the 24-hour ambulatory blood pressure measurements, are too demanding for the patient cohort under study. Patient screening interviews conducted by the clinical study coordinators reflected this notion among the majority of patients potentially eligible for study inclusion.**

[figure not shown]
**Therefore, to increase enrollment, we amend the protocol to make optional the 24-hour ambulatory blood pressure monitoring, thus focusing on the weekly in-office blood pressure measurements as described below to screen primarily for the risk of blood pressure elevation.**

A similar approach to risk detection was taken in the largest prospectively randomized clinical study on NSAIDs (Nissen SE et al. N Engl J Med. 2016 Dec 29;375(26):2519-29.

CONFIDENTIAL

Cardiovascular Safety of Celecoxib, Naproxen, or Ibuprofen for Arthritis. PMID: 27959716) where patients with osteoarthritis or rheumatoid arthritis and with elevated cardiovascular risk or established cardiovascular disease received either a high dose of ibuprofen or naproxen or a low to medium dose of celecoxib. Data on blood pressure suggests that less than 0.1% of patients exposed to NSAIDs experience hypertensive urgencies or emergencies at 45 days into dosing, which is the planned duration of celecoxib exposure for the current study. The incidence of blood pressure related events did not exceed 0.6% after 30 months of NSAID treatment.

Time to first hospitalization for hypertension in PRECISION (Ruschitzka F et al. Differential blood pressure effects of ibuprofen, naproxen, and celecoxib in patients with arthritis: the PRECISION-ABPM (Prospective Randomized Evaluation of Celecoxib Integrated Safety Versus Ibuprofen or Naproxen Ambulatory Blood Pressure Measurement) Trial. Eur Heart J. 2017 Nov 21;38(44):3282-3292. PMID: 29020251)

Regression lines were added manually per visual inspection to extrapolate the NSAID-exposure-related event risk at 45 days of administration.

**In the case that patients opt in for the 24hr APBM, patients' activity patterns during the 24 hour ABPM sessions, in particular in- and out-of-bed times to differentiate the diurnal profile of blood pressure changes during day- and nighttime, will be recorded by two different methods, paper and pencil logs and body actigraphy.**

CONFIDENTIAL

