This material is the property of the University of Pennsylvania.

**In-office blood pressure measurements (in triplicates 5 minutes apart after a 5 minute resting period) will continue at weekly intervals throughout the study. In the case that all systolic blood pressures taken on  $\geq 2$  separate office visits are  $\geq 150$  mmHg systolic blood pressure or  $\geq 90$  mmHg diastolic blood pressure, a follow up 24-hour ABPM will be scheduled within one to two weeks. Here, the same criteria for study exclusion, as outlined above, will be applied.**

The reference systolic and diastolic blood pressure of 150/90 mmHg in people aged 60 years and older has recently been recommended in the “JNC8 evidence-based guideline for the management of high blood pressure in adults 2014” (30).

**In the case that patients opt in for the 24hr APBM, the benefit to patients is the extensive phenotyping of their blood pressure response to celecoxib. Patients exhibiting an above average blood pressure response to celecoxib will be advised to be cautionary in particular when taking over-the-counter or prescription NSAIDs for longer periods of time. In addition, the primary care physician will be advised to monitor blood pressure in such patients.**

A challenge will be the high prevalence of hypertension in this age group, estimated at approximately 65% of men and 75% of women by age 70 years (31). Study enrollment can be offered to this patient cohort provided that blood pressure is adequately controlled with life style changes and/or anti-hypertensive pharmacotherapy. This option will also be offered to patients initially excluded from the study or excluded from the study due to elevated blood pressure. Here, the benefit to patients is that their blood pressure is monitored over periods of 24 hours on multiple occasions, a diagnostic tool less common in the primary care setting. This is expected to actively engage patients in the control of their blood pressure, which is beneficial across all ages (32).

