## 12 Appendix

### 12.1 Study Flow-Chart

Procedures conducted with all participants				
Procedure	Phone Screen	In-person Screen	Baseline	Week 6
Informed Consent		X (Initial screening consent)	X (Full study consent)	X
Verbal Consent	X			
Screen, History (include GI/bleeding risks)	X			X
Screen, History, SCID, MADRS, HAMD, CGI, MOCA		X		
EKG		X		X
PE , Laboratory tests, including IL-6, IL-10, CBC with diff;		X	X	X
MRI; structural and functional			X	X
Lifetime depression, PSS, LES score			X	
Framingham VRF, CIRS-G, QOL		X		X
Neuropsychological tests (COWA, Trails A & B, WLMT, Digits Forward, Digits Backward, Digits Ascending, MMSE, Logical Memory, Digit Symbol, Benton Visual Retention, Shipley Vocabulary, Boston Naming, CogState)			X	X

\*.

CONFIDENTIAL

This material is the property of the University of Pennsylvania.

Additional procedures conducted with depressed participants initially randomized to celecoxib:					
Procedure	Study Visits				
	Baseline	Wk 1	Wk 2	Wk 4	Wk 6
Concomitant Medications	X	X	X	X	X
Drug Dispensed Escitalopram + celecoxib or escitalopram + placebo (weeks 0-6)	X	X	X	X	X
Psychiatrist evaluation, depression scales, Vital Signs (including optional urine samples at baseline, week 1 or 2, and 6; triplicate in-office BP weekly and monitor GI-pain/bleeding for safety ),AEs, SAEs	X	X	X	X	X
PE (Lab tests including IL-6, IL-10, CBC with diff)	X	X	X	X	X
Liver function test & GI/bleeding risks	X		X		
Actigraphy (1 consecutive day minimum, optional longer),		X	X	X	
Optional Stool Sample	X		X		X
Optional Saliva samples	X	X	X	X	X
Safety (ABPM, FOBT and/or hematocrit levels)	X		X		
Safety (24-hour dietary recall, optional counseling on sodium-deplete diet)	X	X			

CONFIDENTIAL

This material is the property of the University of Pennsylvania.

	Additional procedures conducted with depressed participants initially randomized to placebo:									
	Procedure			Phase 1			Open Label Phase			
	Baseline	Wk 1	Wk 2	Wk 4	Wk 6	Wk 1	Wk 2	Wk 4	Wk 6	
Concomitant Medications	X									
Drug Dispensed Escitalopram + celecoxib or escitalopram + placebo (weeks 0-6) (Open label- Escitalopram + celecoxib)	X	X	X	X	X	X	X	X	X	
Psychiatric evaluation, depression scales, Vital Signs (including optional urine samples at baseline, week 1 or 2, and 6; triplicate in-office BP weekly and monitor GI-pain/bleeding for safety ),AEs, SAEs	X	X	X	X	X	X	X	X	X	
Liver function test & GI/bleeding risks	X		X				X			
Actigraphy	X	X	X	X	X	X	X	X	X	
Optional Saliva samples	X	X	X	X	X	X	X	X	X	

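### With 24-hour blood-pressure monitoring now optional, the only numeric on-treatment stopping rule cannot be evaluated for a participant who has no baseline recording and a triggered daytime systolic mean of 150 mmHg or more

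*Combined protocol and SAP*

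**What the plan says.** All places are in the combined protocol and SAP.

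- **Stopping criteria (10.5.2).** Under the initial strategy, trial medication was stopped when two things held together. Mean daytime and nighttime systolic pressure had to be up by 10 mmHg, "compared to the mean daytime and nighttime systolic blood pressure at baseline and the mean daytime (that is out of bed times") systolic pressure had to be at least 150 mmHg.
- **Amendment (10.5.2).** Because enrolment was very slow, "we amend the protocol to make optional the 24-hour ambulatory blood pressure monitoring". Section 5.4 agrees: "Participants may also have 24-hour ambulatory blood-pressure monitoring".
- **Current trigger (10.5.2).** Office readings, taken in triplicate, "will continue at weekly intervals throughout the study". If they are all at or above 150 mmHg systolic or 90 mmHg diastolic at two or more visits, "a follow up 24-hour ABPM will be scheduled within one to two weeks", and then "Here, the same criteria for study exclusion, as outlined above, will be applied".
- **Flow chart (12.1).** One row, marked at baseline and week 2, reads "Safety (ABPM, FOBT and/or hematocrit levels"). Another carries the label "triplicate in-office BP weekly" but is marked only at baseline and weeks 1, 2, 4 and 6.
- **Visits (2.2, 5.2).** On-treatment visits are at weeks 1, 2, 4 and 6, and the open-label phase repeats them. Section 10.4 says blood pressure is taken at each visit.

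**The concern.** The amendment removed the guarantee of a baseline ABPM but kept a stopping rule that uses it as comparator. Office readings cannot stand in for it, since they give no nighttime mean, and no substitute comparator is stated.

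The gap opens where the rule is most needed: a participant on celecoxib or its placebo whose raised daytime pressure has just been confirmed by ambulatory recording. The protocol then does not say whether to stop. Section 10.4 lists blood-pressure monitoring among the precautions behind its minimal-risk statement for celecoxib, so a rule that gives no answer in that situation matters for safety.

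A secondary matter is that 10.5.2 and the flow-chart label call the office screen weekly, while no visit falls in week 3 or week 5.

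**Working it through.** No power or alpha figure is involved. The check is one of logic and of calendar.

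**1. Is the rule in force?** The criteria are described in 10.5.2 as part of the initial strategy, but the later, current paragraph on office readings expressly applies them to the triggered ABPM. They are not superseded.

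**2. Is a baseline ABPM assured?** No. Sections 10.5.2 and 5.4 make it optional. The flow-chart row can be read in two ways: any one of ABPM, occult-blood test or hematocrit suffices, or ABPM is listed together with one or both of the blood-loss tests. Even the second reading does not make mandatory what 10.5.2 makes optional.

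**3. What does the rule return?** Condition A: rise of at least 10 mmHg over the baseline daytime and nighttime means. Condition B: daytime mean of at least 150 mmHg. Stop only if A and B both hold. With illustrative readings:

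| Triggered ABPM, systolic day/night | Baseline ABPM, systolic day/night | Rise day/night | A | B | Result |
|---|---|---|---|---|---|
| 145/130 | none | unknown | unknown | no | not met |
| 155/140 | none | unknown | unknown | yes | undetermined |
| 155/140 | 148/133 | 155−148 = 7; 140−133 = 7 | no | yes | not met, continue |
| 155/140 | 140/125 | 155−140 = 15; 140−125 = 15 | yes | yes | met, stop |

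The last three rows have the same triggered reading. Which of continue or stop applies depends wholly on the baseline value. So the missing comparator decides the outcome exactly when B holds, and is irrelevant when B fails. Taken literally, a participant in the second row has not been shown to meet the criteria and stays on study drug.

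**4. When can the triggered ABPM fall?** The course is 3 + 39 = 42 days (2.2, 4.2). Visits at weeks 1, 2, 4 and 6 are days 7, 14, 28 and 42. Taking two weeks as the outer limit with no minimum delay, the latest date is the day of the second raised visit plus 14:

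- baseline and week 1: 7 + 14 = day 21, with 42 − 21 = 21 days of dosing left (uncommon, because 2.8 caps entry pressure at 150/90 mmHg);
- weeks 1 and 2: 14 + 14 = day 28, with 14 days left;
- weeks 2 and 4: 28 + 14 = day 42, with none left;
- weeks 4 and 6: between day 42 and 42 + 14 = day 56.

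These are latest dates, not expected ones. Section 10.5.2 also gives 45 days as the planned celecoxib exposure; on that figure 45 − 42 = 3 days of dosing would remain at day 42. For weeks 4 and 6, a non-remitter first randomized to placebo could already be on open-label celecoxib when the ABPM is done.

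**5. Weekly against the schedule.** Six on-treatment weeks less visits at weeks 1, 2, 4 and 6 leaves weeks 3 and 5 without a scheduled reading, in each phase.

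**The case against.** The strongest reply is that the participant is not unmanaged. The investigator and coordinator watch vital signs and the investigator may adjust dosage (2.2). The medical monitor reviews each participant's course (7.6.1.2), and the DSMB sees office and ambulatory pressures (7.6.1.3). A raised reading that leads to further testing arguably counts as an adverse event (7.1.1), to be followed to resolution or stabilization (7.2). At a single center this also limits inconsistent handling. All of that stands, and a reader who infers that such a participant has no protection would be wrong. But none of these provisions gives a numeric on-treatment limit or a comparator.

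Section 10.5.2 also tells controlled hypertensives that they will have 24-hour recordings on several occasions. This is current text about a subgroup likely to be affected. It is worded as a benefit of taking part, and does not require a baseline recording.

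A reader might want a head-count, by applying the 7–17% above-average responses quoted in 10.5.2 to the celecoxib arm with some assumed share of missing baselines. The documents do not support that. The percentage uses another definition (a rise of 20 mmHg and systolic pressure above 140 mmHg) in older people, whereas the trial enrols ages 18–80, and no missing-baseline rate is given.

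A reader might also infer that confirmation always comes too late. The calendar does not show this: early triggers leave dosing time, and the end of exposure is itself given inconsistently.

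**Conclusion.** The point holds in a narrow form. The protocol's only numeric on-treatment blood-pressure stopping rule cannot be evaluated for a participant who has no baseline ABPM and whose triggered ABPM shows a daytime systolic mean of at least 150 mmHg. Read literally, that participant continues celecoxib or placebo.

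Reaching this branch takes a missing baseline ABPM, raised readings at two or more visits, and a triggered daytime mean at or above the limit. How many participants that would be is unknown. Missing baselines are foreseeable, since 10.5.2 made ABPM optional after only 2 patients enrolled in 2 years and patients found it too demanding.

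The conclusion rests on reading the two criteria as jointly required, as 10.5.2 words them, and on the optional status in 10.5.2 and 5.4 governing the flow chart. It does not extend to participants with a baseline ABPM, to daytime means below 150 mmHg, or to any efficacy analysis. It is a cheap patient-safety improvement. The weekly mismatch is a secondary wording conflict and adds little to the weight of the point.

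**What to change.** In 10.5.2, add two statements:

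1. Where no baseline ABPM exists, a mean daytime systolic pressure of at least 150 mmHg on the triggered ABPM is sufficient to discontinue celecoxib or placebo.
2. The triggered ABPM is done as soon as possible and, where feasible, before more study drug is dispensed.

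The cost is amendment wording. Because 2.8 admits pressures up to 150/90 mmHg and 10.5.2 welcomes controlled hypertensives, a few participants already close to 150 mmHg at entry may stop without a true on-treatment rise.

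The alternatives are less attractive. Requiring a baseline ABPM of everyone would close the gap but undo the amendment made to rescue enrolment. Using baseline office triplicates as comparator would keep a change criterion, but sets office against ambulatory values and supplies no nighttime mean.

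Separately, reconcile the weekly wording in 10.5.2 and 12.1 with the visit schedule and with 10.4. This should not be taken as grounds for fewer readings. Office pressure is now the primary screen in place of mandatory ABPM, so adding a pressure check at weeks 3 and 5 follows the amendment's intent more closely than deleting the word, at the price of two extra contacts per phase.

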#### **10.5.2 Blood pressure**

The risk of NSAIDs to induce hypertension (12, 13), sodium retention (13) and edema (13) is well recognized (14-17), but it remains unclear why some patients develop such complications and others do not. Factors associated with this risk are age, co-morbidity, preexisting hypertension and elements of drug exposure to selective COX-2 inhibitors. Latter includes dose, attained plasma concentrations, duration of action and dosing and the degree of selectivity for COX-2.

Retrospective analyses of blood pressure responses have been performed in most NSAID trials of large populations and/or those involving extended drug exposure, although these are usually not based on rigorous (or, in some cases, not even pre-specified) blood pressure measurements. In some studies, the incidence of hypertension has been recorded merely as reported adverse events or by retrospectively defined changes from baseline. Based on these assessments, all NSAIDs have increased blood pressure or induced hypertension within diverse study populations, although this appears to relate to COX-2 selectivity (confounded with drug exposure; (9)). Perhaps unsurprisingly, the rates in blood pressure increase were highly variable across studies and conditioned by the specific characteristics of the study population and by recording methods. However, the lack of information from rigorously designed and sufficiently sized trials limit any conclusions about the relative likelihood of hypertension on specific inhibitors or in subpopulations.

Only a small number of clinical trials – some of which were not powered to detect small changes – have assessed prospectively the effects of COX inhibition on blood pressure control. Of note is that young, healthy individuals are unlikely to experience an increase in blood pressure in response to traditional (t)NSAIDs, such as naproxen or ibuprofen or purposefully-designed, selective COX-2 inhibitors, like rofecoxib or celecoxib based on these studies. Older, normotensive subjects and patients with controlled, stable hypertension can be expected to have average increases of 3-5 mmHg in systolic blood pressure (18-22) with an incidence of above average responses (as defined by an increase of 20 mmHg in systolic blood pressure and a systolic blood pressure above 140 mmHg) ranging from 7-17 %. As one would expect,

CONFIDENTIAL

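### The office blood-pressure screen can refer a participant for ABPM on diastolic pressure, but the exclusion criteria then applied to that ABPM are systolic only.

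*Combined protocol and SAP*

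**What the plan says.** All the relevant text is in Section 10.5.2 (Blood pressure) of the combined protocol and SAP.

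- **Literature summary.** Average systolic rises of 3–5 mmHg are expected in older normotensive subjects and in patients with controlled, stable hypertension. Above-average responses are described "as defined by an increase of 20 mmHg in systolic blood pressure and a systolic blood pressure above 140 mmHg".
- **Initial strategy.** Its purpose was "to identify the patients responding to celecoxib administration with an above average increase in blood pressure", by ABPM at baseline and again after one to two weeks. The criteria for stopping trial medication and leaving the study concern "Patients demonstrating an elevation of 10 mmHg in mean daytime and nighttime systolic blood pressure at 1-2 weeks after the start of the study", relative to baseline, and also require that "the mean daytime (that is out of bed times) systolic blood pressure is" at or above 150 mmHg.
- **Amendment.** ABPM became optional because of poor enrolment. Office measurements became the primary screen for blood-pressure elevation.
- **Current office rule.** The trigger sentence takes all systolic pressures from two or more separate visits as its subject. It sets a limit of ≥150 mmHg systolic or, in its words, ≥90 "mmHg diastolic blood pressure, a follow up 24-hour ABPM will be scheduled within one to two weeks". The next sentence brings the earlier criteria back: "Here, the same criteria for study exclusion, as outlined above, will be applied".

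The entry ceiling in Section 2.8 is 150/90 mmHg, so diastolic 90 is a limit that the protocol uses elsewhere too.

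**The concern.** A screen followed by a confirmatory measurement works only if the second step can act on what the first step found. Here the first step looks at systolic and diastolic pressure, and the second has a numeric rule for systolic pressure only. The trigger sentence is also defective in itself, because it gives a diastolic limit to a set of systolic readings. Staff cannot tell from it which diastolic readings count, or whether all of them must exceed the limit.

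The stake is participant safety. Section 10.4 calls blood pressure a possible surrogate for the thrombotic risk of celecoxib, and it lists blood-pressure monitoring among the precautions behind its statement that adding celecoxib is not a greater than minimal risk. With ABPM optional, the office rule and its follow-up are the main numeric safeguard.

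**Working it through.** The documents give no figure to reproduce. The check sets the conditions side by side and runs cases through them. SBP and DBP are systolic and diastolic pressure in whole mmHg, and Δ is the change in SBP from baseline. A rise of 10 or 20 mmHg is read as at least that much.

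| Condition | Systolic part | Diastolic part |
|---|---|---|
| T: office trigger, ≥2 visits | SBP ≥150 | or DBP ≥90 |
| S: exclusion criteria on ABPM | Δ ≥10 (day and night means) and daytime SBP ≥150 | none |
| A: *above average* in the literature summary | Δ ≥20 and SBP >140 | none |

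For T, the sentence is read as it was presumably meant, with each limit applied to its own readings.

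**Step 1: diastolic referral.** Office readings are 140/100 at two visits.
- T: 140 < 150, but 100 ≥ 90, so an ABPM is scheduled.
- The ABPM confirms 140/100. S needs daytime SBP ≥150, and 140 < 150, so S is not met.
- DBP does not appear in S, so no diastolic value can change this result. The participant is stopped under S only if the two systolic criteria are also met.

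**Step 2: systolic referral, for contrast.** SBP goes from 135 to 150 with DBP 80.
- T: 150 ≥ 150, so it is met.
- S: Δ = 150 − 135 = 15 ≥ 10, and 150 ≥ 150, so it is met. The systolic limb can be confirmed and acted on.

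**Step 3: the undefined term.** Suppose that A is what *above average* means, that DBP is below 90, and that office values and ABPM means are similar.
- A requires SBP >140, while T and S both require SBP ≥150. SBP of 141–149 can therefore meet A and must fail both T and S. Baseline must then be at least 20 lower, so at most 149 − 20 = 129.
- Example: 118 to 146. Δ = 146 − 118 = 28 ≥ 20 and 146 > 140, so A is met. 146 < 150, so T and S are not.
- At the edge: 129 to 149. Δ = 20 and 149 > 140, so A is met. 149 < 150, so T and S are not.
- The reverse also occurs. In Step 2, Δ = 15 < 20, so that participant meets S but not A.

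Step 1 does not depend on the assumptions in Step 3, and it holds even where a baseline ABPM exists and the follow-up ABPM is on time.

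**The case against.** The strongest reply is that a broad screen followed by a narrower confirmation is a legitimate design. The diastolic limb does have a consequence, since it leads to a 24-hour ABPM, and a participant referred that way may still meet the systolic criteria. All of this is right, and a reader who infers that the diastolic limb leads nowhere goes too far. It does not answer the narrower point: the confirmatory rule cannot act on the pressure that prompted the referral.

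It can also be said that the systolic criteria belong to an abandoned strategy. The strategy was replaced, but the current office rule expressly reinstates its exclusion criteria.

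Other oversight remains. The investigator monitors vital signs and may adjust dosage (Section 2.2), the medical monitor reviews the study course (Section 7.6.1.2), and the DSMB reviews office and ambulatory pressures (Section 7.6.1.3). These are real protections, and failing a numeric cut-off is not the same as going unnoticed. None of them supplies a numeric rule that closes the gap.

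On *above average*, a reader might infer that the protocol has three competing definitions of a response and misses the very patients it set out to find. The documents do not support that. The 20 mmHg definition describes published trials and is not adopted as a trial rule. The purpose quoted above belongs to the initial strategy, and only its exclusion criteria were carried forward. A 10 mmHg rise is itself above the 3–5 mmHg average in the ordinary sense. The term is also used in the advice to participants who opt in to ABPM. What stands is that neither use says which meaning applies.

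**Conclusion.** The safeguard is wrong as written: the trigger has a diastolic limb, the exclusion criteria applied after it do not, and the trigger sentence attaches a diastolic limit to systolic readings. This follows from the current text alone. The ambiguity over *above average* is secondary. The 141–149 mmHg gap exists only if the literature definition is meant, diastolic pressure stays below 90, and office and ABPM values are similar.

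The number of participants affected cannot be derived. A reader might apply the published incidence, "ranging from 7-17" %, to the celecoxib arm or to all depressed participants. That would not measure this defect, for three reasons:
- The rate counts everyone who meets the literature definition, including those at or above 150 mmHg whom the trigger can catch. The share at 141–149 mmHg, or with a mainly diastolic rise, is not given.
- It relates to older normotensive subjects and patients with controlled hypertension. The trial enrols from age 18, and the same section expects little effect in young, healthy people.
- Not all 100 depressed participants will receive celecoxib. Of those starting on placebo, only non-remitters move to it (Section 2.2).

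**What to change.** Reconcile the exclusion criteria and the office rule within Section 10.5.2:

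1. Rewrite the trigger sentence so that the systolic and diastolic limits each apply to their own readings, and say whether all readings at the visits must exceed the limit.
2. State what follows when the diastolic limb triggers an ABPM and the ABPM confirms the diastolic elevation.
3. State what *above average* means where it is used for the safeguard and for advice to participants, and whether the definition in the literature summary applies.

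The trigger and the stopping rule may keep different thresholds. Choosing them, and the action attached to each, is for the investigators and the DSMB. No value or action is proposed here. The cost is a wording amendment, and the reconciliation in itself needs no new visits or devices.
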